Behavioral interventions such as calorie restriction, exercise, and behavior modification are key elements to successful, sustained weight loss. Three behavior modification techniques will be key elements in the Lifestyle Balance Program: (1) motivational interviewing and (2) contingency contracting, and (3) social skills training provided by the Lifestyle Balance coaches. These will be described in the Methods section below. In fact, behavioral interventions have been used successfully to prevent diabetes and demonstrated efficacy equal to the anti-diabetic medication metformin (43). Behavioral interventions may be an excellent option for the SMI population given the relative risks of any of the above strategies discussed — switching antipsychotics to a potentially ineffective one, adding medications with additional toxicities and propensities to worsen psychiatric symptoms, and finally surgery that is risky in patients whom surgeons feel will not benefit from such intervention. Most publications on weight loss in the SMI population to date are neither controlled nor large, but offer some hope that behavioral strategies can be of assistance to patients with psychotic disorders. In one small 14-week study, (N=14) patients achieved, on average, 10 pounds of weight loss when given behavioral interventions (classes and a contingency model—rewards for weight lost) compared to a control group (44). Retrospective analysis of simple interventions we have offered in clinic suggest behavioral interventions such as simply weighing patients, meeting with a nutritionist, maintaining a food diary, and encouraging exercise were fairly successful in RIS and OLZ treated subjects, although these strategies seemed to have little effect in CLOZ treated subjects (11).

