In summary, our ongoing research has been quite successful at achieving weight loss. It is to our knowledge, the longest term intervention proven effective in SMI patients (often dually diagnosed with substance abuse) with antipsychotic medication associated obesity. This program may close a gap in care for those patients who cannot or do not access MOVE!. Continuation of this work is crucial to see if we can optimize the maintenance effects of this program as well as disseminate this work.

V. Research Design and Methodology

A. The study is a multi-site, randomized, open, effectiveness trial with masked raters blind to treatment condition. 120 veterans (30 at each of 4 sites) will be randomized for participation in this study. The 4 sites and primary Co-investigators are:

West Los Angeles VAMC	Brentwood, CA	[name]
Long Beach VAMC	Long Beach, CA	[name]
Sepulveda, VAMC	North Hills, CA	[name]
Los Angeles Ambulatory Care	Los Angeles, CA	[name]

B. The oversight and organization of the multicenter trial across all 4 sites will be coordinated by [name] as the Principal Investigator and her Program Manager located at the West Los Angeles site. At each of the 4 sites there is a designated co-investigator who will be responsible for weekly team meetings of all research staff that will encompass clinical and research issues. The overall PI will arrange a study start up meeting and monthly coordinating meetings to facilitate fidelity of the project between all 4 sites. Weekly coordinating meetings will be necessary during the first 6 months of start up.

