E. Procedures for the Usual Care Group: As most psychiatrists are being advised to counsel patients on weight, diet, and exercise, Usual Care will be only some modest counseling. Referral to the MOVE program by their treating psychiatrist would not be discouraged. Patients will be encouraged to exercise and eat a healthy diet, and will be weighed at each visit. No classes on nutrition and no exercise classes will be given to these patients as part of this program. Patients in usual care will be seen on the same schedule as the experimental group, in order to equalize contact time. At every visit, patients will complete a questionnaire about their knowledge of healthy eating habits and nutrition. After 6 months, if patients in the “usual care group” wish to participate in the more rigorous behavioral weight loss program they will be given that opportunity. A de-identified photograph of each participant’s body from the neck down will be taken during visit one and at the end of study.

SCHEDULE OF EVENTS

Visit	Time	Rater	0	1-7	8	9	10	11	12	13	14	15	16	17	18
Week			0	1-7	8	12	17	21	26	30	34	38	43	48	52
Month			0		2	3	4	5	6	7	8	9	10	11	12
Visit Log/Assessment Packet	--	--	X	X	X	X	X	X	X	X	X	X	X	X	X
AHA Exercise Risk Stratification	10	MD	X												
Brief Psychiatric Rating Scale (BPRS)	15	MD	X		X				X						X
CGI	5	MD	X		X				X						X
Hamilton Depression/ Beck Anxiety Scale	20	MD	X		X				X						X
Physical Exam	15	MD	X												X
Structured Clinical Interview for DSM-IV (SCID)	15	MD	X												
Antipsychotic Side-effects Checklist (ASC)	5	C	X		X				X						X
Assessment of Patient Food Preparation Activity	5	C	X		X				X						X
Biopsychosocial/Spiritual Wellness Self Appraisal (BPSS)	5	C	X		X				X						X
Demographics	10	C	X												

EXIT interview	5	C														X
Fidelity Checklist Change Assessment	10	Proj. Mgr	X						X							X
Framingham Hard Coronary Heart Disease	5	C	X													X
Healthy Lifestyle Balance Knowledge Quiz	15	C	X		X				X							X
Informed Consent Video	30	--	X													
Informed Consent Quiz	15	C	X						X							X
Labs: Lipid Profile, fasting glucose, HgbA1C, insulin/ HOMA calculation, c-reactive protein, microalbumin, creatinine	10	Lab	X		X				X			X				X
Lifestyle Habits Questionnaire	10	C	X	X	X	X	X	X	X	X	X	X	X	X	X	X
Motivational Interview	5	C	X		X				X							X
Quality of Life Scale	15	C	X													X
SAIQ- Insight Measure	10	C	X		X				X							X
Telephone Contact Assessment (as needed)	5	C														

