Lifestyle Balance Coaches and physicians will meet as a team to discuss patients who need additional interventions to meet their expected dietary changes and exercise goals. We have developed a flow chart that our Lifestyle Balance Coaches will utilize to assist patients with adherence to the program. The number and types of interventions required to assist patients in making healthy lifestyle changes will be tallied. For the most part, these are the modalities described in the grant that can be ascertained in an objective manner for data analysis purposes. Lifestyle coaches' adherence to the training program will be assessed by a simple fidelity measure and an independent objective consultant who will randomly observe coaches meeting with veterans in the lifestyle balance intervention group.

Because weight gain can be a deterrent for patients to adhere to antipsychotic medications, one of our hypotheses is that people in the lifestyles intervention group will have higher rates of adherence to their psychiatric medications than patients in the "treatment as usual" group. We will rely primarily upon the VA computerized record system to determine the percent of psychiatric appointments attended by patients as well as the percent of medications refilled. In addition, we have developed and will utilize several objective measures of adherence to treatment.

J. Additional Interventions: In the event that the patient is not losing weight or is unable to adjust to their diet or exercise regimen, we will request the patients permission for additional intervention so that we may assist them adhere to their exercise and diet. Additional interventions are optional and may include:

1. Additional Exercise Interventions

- a. The research physician will review the patient's medical chart to determine if their current medications may be contributing to fatigue, sedation, and/or lack of motivation. Consultation with the patient's treating psychiatrist may lead to suggestions about medication adjustments to be made by the treating psychiatrist (as it would be done in usual care) to optimize energy and motivation of patients.
- b. The patient's rewards may be adjusted to optimize their motivation to exercise (See DPP Toolbox Appendix).
- c. The patient's exercise goal expectations may be adjusted.

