if in the opinion of the investigator, weight changes and/or metabolic changes warrant intervention that is more rigorous.

M. Rater Reliability: Rater reliability is maintained by all raters co-rating patients in reliability sessions. A start up meeting will include co-rating sessions to assure reliability of assessors. All psychiatric raters have undergone inter-rater reliability quality assurance testing on a yearly basis as part of their ongoing work in clinical trials research. Raters will be assigned specific patients and will be expected to rate that same patient throughout the year. Raters will be masked to randomized condition.

N. Statistics and Data Analyses

1. General Data Analysis Issues: Data Management:

A. Organization of the Data Core support ([name] Ph.D., Director, [name] senior statistician)

The multi-site study data will be managed locally at each site and will be supported by the VISN -22 MIRECC Biostatistics Core (VISN-22 MIRECC P.I. [name], M.D.) . Affiliation with the VISN-22 MIRECC Core provides the research team with expert general and specialized consultation. The Core also includes statisticians, database and MS Windows applications development programmers and other research support staff. [name] has utilized the core for other multi-site studies she has developed. Both she and her colleague, [name] in Long Beach have experience with the proposed web based data management system.

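### Raters are declared masked, but the plan's meeting rules contradict this and nothing protects the masking of the rater-scored mental health outcomes

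*Combined protocol and SAP*

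**What the plan says.** Section V.A describes an "open, effectiveness trial with masked raters blind to treatment condition". Section V.M repeats the promise, "Raters will be masked to randomized condition", and adds a continuity rule: "Raters will be assigned specific patients and will be expected to rate that same patient throughout the year".

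Other parts of Section V bear on whether that promise can be kept:

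- **V.B (oversight across the four sites)** makes each site's co-investigator responsible for "weekly team meetings of all research staff that will encompass clinical and research issues".
- **V.I (Exercise Opportunities)** states that "Lifestyle Balance Coaches and physicians will meet as a team to discuss patients who need additional interventions" to reach their diet and exercise goals.
- **V.J (Additional Interventions)** lists, among optional steps for patients who are not losing weight or not adjusting to their regimen: "The research physician will review the patient's medical chart to determine if their current medications may be contributing to fatigue" and related problems.
- **V.L (Minimizing Risks)** lets usual-care patients take open treatment after six months if the investigator judges that their weight or metabolic changes warrant it.
- **The Schedule of Events** codes the BPRS, CGI and Hamilton as MD.
- **V.C (Inter-rater Reliability)** names the BPRS, CGI, Ham-D and QOLS as the scales that need rater reliability.

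Section I.D puts mental health outcomes in primary hypothesis (c). The statistical plans in V.N carry the same content under (b).

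**The concern.** Patients and coaches in this trial know the allocation. The only protection for an observer-scored outcome is therefore to keep the observer from learning the arm. The plan declares this protection but never says how it is achieved, and two of its standing procedures work against it.

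At stake are the interviewer-rated measures of psychopathology and quality of life. A rater who knows the arm, and who may expect the program to help, can score a borderline answer more favorably without meaning to. The bias would run in the direction of the primary hypothesis. The mixed model could not remove it, because it would look like a treatment effect. A report that repeated the masking claim would also give readers more assurance than the conduct of the trial supports.

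**Working it through.** No arithmetic applies. The check sets the masking statements beside the procedures and asks whether a rater who follows every rule as written could stay masked.

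**1. The weekly meetings (V.B against V.A and V.M).** The meetings cover clinical as well as research matters, and the attendance rule is all research staff. Raters are research staff, and neither V.B nor V.M exempts them. Clinical discussion of patients in a two-arm behavioral trial will readily show who is attending classes and who is not. This applies to every rater, including whoever scores the QOLS.

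**2. The coach-physician meetings (V.I against the Schedule of Events).** The patients discussed are those falling short of diet and exercise goals. Such goals are set under the Lifestyle Balance procedures in V.D. Under V.E, usual care is modest counseling with no classes. At least until usual-care patients may take open treatment after month 6, being discussed at this meeting all but identifies a program patient. Physicians attend, and the three main psychiatric scales are assigned to MD. The plan does not separate the two groups of physicians.

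**3. Other physician roles (V.J and V.L).** Chart review for a patient struggling with the regimen, and the judgment on open treatment for a usual-care patient, both bring the decision-maker close to the allocation. The second requires knowing it. The plan does not bar the patient's rater from either role.

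**4. Persistence (V.M).** The BPRS, CGI and Hamilton are scheduled at baseline, week 8, month 6 and month 12. With one rater per patient, a disclosure before week 8 affects all three post-baseline ratings, and one between week 8 and month 6 affects two. The Quality of Life Scale is scheduled only at baseline and month 12, so a disclosure at any time in the year affects its only follow-up value.

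**5. Search for a safeguard.** The plan describes taped reliability interviews, six-monthly drift checks, co-rating sessions and coach fidelity checks. These address agreement between raters and delivery of the program. The plan has no separate assessor team, no rule on meeting attendance, no instruction to patients about not revealing their arm, and no log or test of unmasking.

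As written, V.A and V.M cannot be reconciled with V.B. Nor can they be reconciled with V.I unless the meeting physicians and the MD raters are different people, which the plan does not say.

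**The case against.** The strongest reply is that this is thin wording, not a failed design, and that the documents never show an unmasked rater. Much of that stands.

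- **Same people?** A reader might infer that the physicians who meet with coaches, review charts or decide on open treatment are the BPRS, CGI and Hamilton raters. No section says so. V.I says only physicians, V.J the research physician and V.L the investigator. A shared MD code does not make them one person, and the chart review is optional. It would go too far to say that the masking claim is false.
- **Quality of life and the motivational interview.** The Schedule gives the same code, C, to the Quality of Life Scale and to a row called "Motivational Interview". A reader might infer that the quality-of-life rater delivers part of the program. The code is undefined and may cover several people. The row lasts five minutes, is not marked by arm and follows the assessment time points, so it may be an assessment form. Classes, goal sheets and diaries carry a separate code, RD, which is a partial separation of delivery from rating.
- **Weight and the quiz.** It is tempting to extend the point to weight, waist, percent fat and the knowledge quiz. These depend little on rater judgment: weight is taken on a common clinic scale at a fixed time of day, percent fat comes from a device, and patients answer the quiz themselves.
- **Other mental health outcomes.** Hypothesis (c) also names the BPSS, which V.G describes as a self-report scale, so it does not rest on observer ratings alone.
- **Design merits.** One rater per patient is a legitimate choice for consistency, and V.E and V.H equalize visits and contact, so visit frequency should not reveal the arm.

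None of this answers the attendance rule in V.B, which covers all research staff, raters included.

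**Conclusion.** The point holds in a limited form. Masking is declared twice, contradicted by the meeting rules and protected by no procedure. The exposure is confined to the rater-scored scales that V.C names: BPRS, CGI, Hamilton and QOLS. The conclusion assumes that sites would run the meetings as written and that patients would be discussed individually at them. The text speaks of clinical issues and does not spell that out.

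The size of any bias is unknown. A reader might try to gauge it from the pilot results in Section IV.E, but those cannot supply it. The 1.2-point fall in BPRS negative symptoms is the program arm's own change, with no usual-care figure beside it. Any amount of rater leniency would have to be assumed, so expressing it as a share of the expected effect would only restate the assumption.

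This should be corrected, because it concerns part of a primary hypothesis and the core of the remedy is a rule about meetings.

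**What to change.** 1. Amend V.B, V.I, V.J and V.M so that anyone who rates the BPRS, CGI, Hamilton or QOLS does not attend the patient-discussion part of the weekly meetings or the coach-physician meetings. Where existing staffing allows, that person should also not coach the patients they rate, review those patients' charts under V.J, or make the judgment on open treatment after month 6 for them.
2. Have each rater record a guess of the patient's arm at month 12, and report the results by arm.
3. Where a measure cannot be separated in this way at a site, describe it as unmasked in the protocol and in the report.

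The attendance rule, the arm guess and the labeling need no new staff. Splitting the physician roles may not be free: the documents name one co-investigator per site and give no count of physicians or assessors. For that reason it is conditional on staffing, with item 3 as the fallback. The remaining costs are some scheduling inconvenience and raters who know less about their patients' clinical course.

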Prior to statistical analyses, the data will be inspected to determine the advisability of scale transformation to normalize distributions or reduce variance heterogeneity (e.g., logarithmic or power transformations) and to identify missing data, outliers, or other unusual features that might bias results. Where multiple measures may overlap or be redundant, preliminary analyses will explore whether it is possible to reduce these using techniques from scale development such as factor analyses. Preliminary analyses are also performed to compare treatment groups on descriptive and clinical characteristics at baseline to ensure randomization has succeeded. If there are significant differences between the treatment groups at baseline we will create propensity scores and include them in all further analyses as covariates to compensate for potential bias. We will also test if there are significant site effects, and if necessary we will include a site variable in the mixed linear model analysis, and model time as nested in subjects and subjects nested in sites.

To address concerns about excessive Type I error rates, the principal analyses are designed to answer clearly stated major research hypotheses, and are based on well-specified dependent variables. The samples are large enough to expect that confidence limits may be reasonably narrow, and findings may be robust enough to permit conservative adjustments of p-values for multiple testing. Bonferroni and other adjustments are necessarily somewhat arbitrary as Saville notes in his argument against their use (71). Additional analyses that are exploratory will be clearly identified as such. All tests will be two-tailed at $\alpha=0.05$.

2. Attrition: Dropout from treatment does not necessarily mean participants will refuse follow-up assessments, and we will attempt to obtain full follow-up data on all enrolled participants regardless of degree of participation and include all enrolled participants in analyses when any outcome data are available (intent to treat). Attrition can compromise randomization, so preliminary analyses will compare baseline characteristics

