3. Repeated measures analyses: We propose to longitudinal (repeated measures) analyses to maximize the additional power we gain by observing the same subjects across 12 months.. Repeated measures analyses permit contrasts at each time point, and also describe and compare trajectories of change (trends), speed and durability of effects. We will also conduct separate cross-sectional to provide outcome data for ongoing safety review, interim progress reports, study oversight and conduct.

The primary design for longitudinal (repeated measures) analyses of continuous outcome scales will be a 2-group (treatment) mixed general linear model of timepoints nested within participants. This is very general linear model that permits flexibility in specifying the nature of the covariances among the dependent measures, allows time-dependent, within and between subject covariates, and permits incomplete (i.e., missing) data. Analyses of trends across the monthly assessments will be done using growth curve model within the mixed model analysis of covariance design with repeated measures described above. We propose to model a linear trend of time unless inspection clearly suggests nonlinearity. By fitting a slope over time (and intercept) for each participant who has baseline and at least one other measure, this method makes good use of all the data, and is robust even if some of the some measures are missing. The use of the mixed general linear model for all cross-sectional and linear hypotheses ensures that results will be comparable across different analyses and provide a framework to include group, person and time-specific covariates if it becomes necessary. The preliminary analyses have shown that this analysis strategy provides meaningful results even with partial data and suggests that we will exceed the originally projected power.**4. Stratification:** Randomization will be stratified by type of antipsychotic and presence of mood stabilizer medication (e.g., depakote, lithium) to assure balance on olanzapine and clozapine by randomizing within three strata – olanzapine, clozapine, and all other antipsychotics -- using three separate randomization lists. Because such stratification can adversely affect statistical power by creating artificially comparable (and heterogeneous) groups, two dummy variables coding olanzapine and clozapine at baseline will be included in all analyses as covariates.

4. Statistical Plans:

Primary Hypotheses:

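### A propensity score enters the models only if baseline tests are significant; the covariate set, including site, should be stated in advance instead

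*Combined protocol and SAP*

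**What the plan says.** **Propensity score (N.1, General Data Analysis Issues).** Preliminary analyses will "compare treatment groups on descriptive and clinical characteristics at baseline to ensure randomization has succeeded". The consequence follows: "If there are significant differences between the treatment groups at baseline we will create propensity scores and include them in all further analyses". No list of baseline variables, number of tests or definition of the score is given.

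**Site (same paragraph).** "We will also test if there are significant site effects, and if necessary we will include a site variable in the mixed linear model". The sentence goes on to describe a nested structure, with visits within patients and patients within sites. No threshold for necessity is given. The Research Design section plans 120 patients, 30 at each of four sites.

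**What is already fixed.** The Stratification paragraph says "two dummy variables coding olanzapine and clozapine at baseline will be included in all analyses as covariates". The Statistical Plans section makes baseline one of the four repeated assessments. The Attrition section will "include all enrolled participants in analyses when any outcome data are available".

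**Stratification.** The paragraph opens: "Randomization will be stratified by type of antipsychotic and presence of mood stabilizer medication". It then achieves this "by randomizing within three strata" (olanzapine, clozapine, all others), "using three separate randomization lists". Mood stabilizer appears in neither the lists nor the two dummies. For the adherence hypothesis, the plan adds a covariate for the baseline stratification medication without saying which medication that is.

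**The concern.** If allocation was carried out properly, baseline differences between arms arise by chance. A significant one is then no evidence that adjustment is needed, and a non-significant one is no evidence that a prognostic variable can be left out. The rule also leaves the content of the primary models unknown until the data have been examined. That sits badly with N.1's own defence against excess type I error, which relies on principal analyses that are specified clearly beforehand.

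The site rule has the same form. Site is a design feature, and the protocol expresses only a hope that exercise options will be comparable across sites.

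The mood-stabilizer mismatch is a separate wording matter. A reader cannot tell whether the randomization had three strata or six.

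At stake are a model known in advance and, to a small degree, power for the between-group main effect.

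**Working it through.** **Inputs from the plan (Power Analysis).** N = 120, attrition 45%, m = 4 data points, f = 0.25, within-subject r = 0.50, two-sided alpha 0.05.

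**1. The plan's figures.** Completers: 120 × 0.55 = 66.
- Main effect: λ = N f² m / (1 + (m − 1) r) = 66 × 0.0625 × 4 / 2.5 = 6.6; F with 1 and 64 df; power 0.716 (stated .7199). With N = 120 it is 0.930.
- Group by time: λ = N f² m / (1 − r) = 66 × 0.0625 × 4 / 0.5 = 33; 3 and 192 df; power 0.999 (stated 0.99). At f = 0.15, λ = 11.88 and power is 0.828 (stated 0.83).

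The figures reproduce and do not depend on this point.

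**2. How often the trigger fires by chance.** The number of tests k is an assumption. For independent tests the chance is 1 − 0.95^k: 0.226, 0.401 and 0.642 for k = 5, 10 and 20. With correlation 0.5 between measures (simulated) it is 0.19, 0.29 and 0.42.

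**3. What the rule does to the main effect.** Simulation on the four-visit mean (variance 2.5/4 = 0.625, difference 0.5 SD, equal arms). One baseline variable is prognostic and the other k − 1 are not. A logistic propensity score is added as a covariate if any t-test has p < 0.05. There were 6,000 runs per cell, so the simulation error is about √(0.7 × 0.3 / 6000) = 0.006. Each entry is power at assumed prognostic R² of 0.10 / 0.30.

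| n, baseline variables | k | No adjustment | Rule, all k in score | Rule, only triggering variables |
|---|---|---|---|---|
| 66, independent | 5 | .709/.714 | .701/.713 | .709/.716 |
| 66, independent | 10 | .722/.716 | .688/.687 | .704/.707 |
| 66, independent | 20 | .713/.718 | .589/.603 | .680/.689 |
| 66, correlation .5 | 10 | .713/.718 | .686/.697 | .706/.720 |
| 66, correlation .5 | 20 | .713/.700 | .633/.633 | .706/.711 |
| 120, independent | 5 | .928/.930 | .929/.941 | .929/.936 |
| 120, independent | 10 | .932/.928 | .928/.937 | .929/.932 |
| 120, independent | 20 | .929/.933 | .892/.926 | .917/.931 |

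Changes run from about +1 to −4 points. The exception is 20 variables all entered at n = 66: −11 to −12 points if independent, −7 to −8 if correlated. Null rejection over all cells was 0.026 to 0.052. A separate single-outcome simulation (n = 66, k = 5 or 10, one variable correlated 0.5 or 0.7 with the outcome) gave 0.027 to 0.038.

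**4. Group by time.** A covariate that is constant over time hardly changes the precision of this contrast. The ratio of its variance with the covariate to that without is 1.000 for complete data and 0.984 to 0.996 with 45% dropout.

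**5. Site.** Four equal sites, a 3-df pre-test at 0.05, site R² assumed to be 0 / .05 / .10. The documents do not say whether the lists run within site, so both cases matter.
- Not balanced by site, n = 66: type I error of the rule .051/.053/.054, with site always in the model .049 to .050. Power of the rule .715/.723/.737, with site always in .693/.716/.737.
- Balanced within site: type I error of the rule .049/.049/.047 at n = 64 and .052/.048/.050 at n = 120. At R² = 0 and n = 64, power is .704 without site and .705 with it.
- Degrees of freedom alone: going from 64 to 61 error df moves main-effect power from 0.7158 to 0.7151.

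**6. Mood stabilizer.** Two crossed factors need 3 × 2 = 6 lists; the paragraph describes three. If mood stabilizer really was a stratum (assumed 40% users, antipsychotic shares 25/15/60, R² .05/.10, n = 66), the model with the two dummies only has type I error .045/.041 and power .722/.725. Adding the term gives power .736/.759, a difference of 1.4 and 3.4 points.

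**The case against.** The strongest reply is that little is harmed. The Power Analysis puts the main weight on the difference in trajectories, and that test hardly moves. Every error or power figure above concerns the between-group main effect and rests on assumed inputs. This stands, and it sets the grade.

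Two further replies also stand. Comparing arms at baseline is not useless: in an open, four-site trial it can reveal that allocation was not carried out as intended. The criticism is only of significance as the trigger for adjustment. And the plan does give a structure for site, with patients nested in sites; what is missing is a commitment to use it.

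A reader might infer that choosing terms from the data inflates type I error. The propensity rule does the opposite. For site, an excess of about 0.4 points appears only if allocation is not balanced within site. The documents leave that open, and under balance the excess disappears, so inflation should not be claimed.

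A reader might also infer that the randomization departed from its design. The operative text (three strata, three lists, two dummies) is coherent without mood stabilizer, so the power cost of 1 to 3 points exists only if that factor was in fact used.

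**Conclusion.** The point holds in a limited form. A propensity score that enters all further analyses only after significant baseline tests is a poor rule, because chance alone would often invoke it and its contents are undefined. The effect is modest: a conservative main-effect test, usually +1 to −4 points of power, and a loss of 11 to 12 points only in the extreme case of 20 independent variables all entered with 66 completers. The analysed number should lie between 66 and 120, because the plan keeps patients with partial data, so that case is unfavourable to the plan. The number of tests, prognostic strength, correlations, site effect and medication shares are all assumptions.

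The site rule is secondary; the reason to change it is a model known before outcomes are seen, not error control. The mood-stabilizer mismatch is a matter of wording. Severity: a change the sponsor could make, not one on which the trial's conclusion depends.

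**What to change.** **N.1, propensity score.** Delete the baseline-significance trigger for the primary models. Report baseline comparisons descriptively; they may still be used to check how allocation was carried out. Keep any propensity-score adjustment as a sensitivity analysis with its variables listed.

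**N.1, site.** State in advance that site is in the model as a design factor, and in which form. The present text describes nesting. Three site indicators would replace it, and with only four sites they avoid estimating a between-site variance from four units. State that no term is added or removed because of a significance test.

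**Stratification paragraph.** Reconcile the named factors with the lists actually used. Add a mood-stabilizer term only if it was in fact a stratum; otherwise remove it as a named factor. Make the covariate for the adherence hypothesis match.

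**Cost.** Wording only. Site as indicators uses three degrees of freedom. The cost in main-effect power is near zero if allocation is balanced within site, and up to about 2 points (0.715 to 0.693) if it is not and site is not prognostic. The olanzapine and clozapine dummies and the baseline assessment stay as planned.
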